9.8.5 Peripheral Biomarkers

Biomarker sample collection will not be applicable per Protocol Amendment 03. However, exploratory analysis of biomarkers on previously collected specimens as detailed below may be conducted.

A variety of biomarkers that may predict or impact the treatment efficacy with bempegaldesleukin and nivolumab will be investigated in peripheral blood specimens taken from all participants prior to and during treatment. Several analyses will be completed and are described briefly below. Additional biomarker assessments may also be performed if samples are available.

9.8.6 Whole Blood for Genetic Analysis

Biomarker sample collection will not be applicable per Protocol Amendment 03. However, exploratory analysis of biomarkers on previously collected specimens as detailed below may be conducted.

Whole blood will be collected from all participants prior to treatment to generate genomic DNA and RNA for Single Nucleotide Polymorphism (SNP)/WES and gene expression analyses, respectively. These analyses will focus on SNPs within genes associated with PD-1, CTLA-4, and

other immunoregulatory signaling pathways to determine if natural variation within those genes is associated with response to nivolumab and bempegaldesleukin treatment and/or with AEs. Also, whole blood RNA will be collected on-treatment to assess for potential changes in peripheral gene expression due to treatment with nivolumab and bempegaldesleukin combinations.

9.8.7 Exploratory Serum and Plasma Biomarkers

Biomarker sample collection will not be applicable per Protocol Amendment 03. However, exploratory analysis of biomarkers on previously collected specimens as detailed below may be conducted.

Blood samples for exploratory serum and plasma biomarker analyses will be drawn at the specified time points indicated in the biomarker table. Additionally, serum and plasma samples will be collected when clinically safe and feasible, upon occurrence of a Grade 3 drug-related AE that results in a dose delay. Separate blood samples will be collected and processed for serum and plasma and then put in frozen storage. Serum and plasma samples may be assessed by ELISA, seromics, microRNA profiling, ctDNA measurements, metabolomics and/or other relevant multiplex-based protein assay methods for immune-related factors that may predict for nivolumab and/or bempegaldesleukin benefit or AEs; such factors may include, but are not limited to levels of soluble PD-L1, anti-tumor antibodies, cytokines, chemokines, inflammatory factors, NKG2D ligands (eg, soluble MICA), circulating tumor DNA, SARS-CoV-2 serologic status, and microRNAs (eg, angiopoietin-2 and fibronectin). Serum and plasma may also be assessed for additional factors that may inform on the etiology of CVA events; such factors may include, but are not limited to those associated with vascular damage (eg, vWF, soluble P-selectin), coagulation and platelet activation (D-dimer, prothrombin 1.2, fibrinogen, solCD40L), eosinophil activation (eosinophil cationic protein) and inflammatory markers relevant to CVA (eg, CRP, TNF α , IL-6, VCAM/ICAM).

9.8.8 Plasma ctDNA

Biomarker sample collection will not be applicable per Protocol Amendment 03. However, exploratory analysis of biomarkers on previously collected specimens as detailed below may be conducted.

Circulating tumor DNA (ctDNA) are small fragments of DNA that are shed from tumor and can be found circulating in the peripheral bloodstream. ctDNA derived from malignant cells can be isolated and analyzed from blood-derived plasma for genetic features including, but not limited to somatic mutations using targeted sequencing-based methods (eg, Next Generation sequencing). To complement the planned genomics analyses outlined for tumor assessments, plasma will be collected at baseline and on-treatment to isolate ctDNA. Mutational data derived from these samples will be compared to those identified directly in the tumor. Baseline and on-treatment changes in mutational burden (either global or individual genes) will be evaluated for association with treatment outcomes. Correlation between mutational burden in blood and the tumor will be explored.

9.8.9 Serum MicroRNA (miRNA)

Biomarker sample collection will not be applicable per Protocol Amendment 03. However, exploratory analysis of biomarkers on previously collected specimens as detailed below may be conducted.

MicroRNAs (miRNA) are widely-expressed, small RNAs that regulate the abundance of mRNA transcripts and their translation into protein. Global miRNA expression profiling has become increasingly common in cancer research, and miRNA signatures that are correlated to stage of disease or to clinical outcomes are now available for a variety of cancer types. Expression profiling of miRNA may be useful also in identifying molecular markers for the prediction of drug responses and for prospective stratification. Intriguingly, miRNAs are stable in serum and may represent miRNAs over-expressed in tumors and/or reflect immune system activity. Serum taken at baseline and during treatment from participants randomized to each treatment arm will be analyzed for miRNA content by microarray or similar methodology. The resulting miRNA profiles will be evaluated for changes in miRNA abundance that occurs following treatment and for associations with response and survival data. Ultimately, the goal will be to determine if unique immunerelevant and/or disease-specific miRNA signatures exist and if they are potentially useful for identifying participants who are likely (or unlikely) to respond to nivolumab treatment.

9.8.10 Myeloid Derived Suppressor Cells

Biomarker sample collection will not be applicable per Protocol Amendment 03. However, exploratory analysis of biomarkers on previously collected specimens as detailed below may be conducted.

Myeloid derived suppressor cells (MDSCs) are an immune cell population capable of suppressing T cell activation and proliferation. Low pre-treatment MDSC levels in peripheral blood may be associated with better overall survival in melanoma participants treated with nivolumab combination. MDSCs will be measured at baseline and on-treatment to assess pharmacodynamic changes or associations with outcome.

9.8.11 Peripheral Blood Mononuclear Cells and Whole Blood Immunophenotyping

Biomarker sample collection will not be applicable per Protocol Amendment 03. However, exploratory analysis of biomarkers on previously collected specimens as detailed below may be conducted.

Whole-blood samples will be collected for isolation and cryopreservation of peripheral blood mononuclear cells (PBMCs) in both arms of the study. These cryopreserved samples may be used for functional activation tests, additional immunophenotyping assays, T-cell receptor sequencing, and DNA methylation.

Whole blood immunophenotyping by flow cytometry will be used to assess pre-treatment and serial on-treatment changes in composition/activation status of peripheral immune cell subsets to determine PD changes and/or association with outcome. Cellular subsets evaluated will include, but not limited to, T, B, NK, natural killer T cell (NKT), and T-regulatory cells. Cellular subsets

may be defined in terms of, but not limited to, memory phenotype, activation, exhaustion, signaling markers, and proliferation status before and after treatment. Several markers may be used to assess this including, but not limited to, Ki-67, human-leukocyte antigen-antigen D-related, CTLA-4, PD-1, ICOS, CD39, etc.

9.8.12 Microbiome Analysis

Biomarker sample collection will not be applicable per Protocol Amendment 03. However, exploratory analysis of biomarkers on previously collected specimens as detailed below may be conducted.

The potential influence of the gut microbiome on melanoma treatment outcome is not known. It is known that the microbiome can affect treatment of certain cancer types (ie, colorectal cancer) through several mechanisms, including promotion of disease via induction of chronic inflammation or catabolism of polyamines on other carcinogenic digestible material. In addition, the innate and adaptive immune system activation state and repertoire may be altered based on local microbiota leading to differential activity of nivolumab in cancer participants. DNA will be extracted from fecal samples taken prior to therapy and on-treatment with nivolumab and nivolumab/bempegaldesleukin combination (Table 9.8.2-2). A gene-sequencing approach will be utilized to survey microbial species in the gut in order to define microbiota as a function of efficacy and safety. Overall changes in the gut microbiota will also be characterized in individual participants that receive therapy.

9.9 Medical Resource Utilization and Health Economics

This section is not applicable per Protocol Amendment 03. Healthcare resource utilization data will be collected for all randomized participants using an internal CRF developed for use in previous trials. The form, which is completed by study staff, records information about hospital admissions, including number of days spent in various wards and discharge diagnosis, as well as non-protocol specified visits related to study therapy, including date of visit, reason for visit, and type of visit. The health care resource utilization data will be used to support subsequent economic evaluations.

10 STATISTICAL CONSIDERATIONS

In general, continuous data will be summarized by descriptive statistics, including number of participants, mean, standard deviation, median, minimum, and maximum. Categorical data will be summarized by the number and percentage of participants. Unless otherwise specified, data will be summarized by treatment arm.

All efficacy evaluations will be analyzed using the intent-to-treat (ITT) population, and all safety endpoints will be summarized using the Safety population.

A detailed description of analysis methods will be provided in the statistical analysis plan (SAP).

The final ORR and PFS analyses, and the first OS interim analysis (combined with the second OS interim analysis) have been completed using the locked database with database lock date of 01-Feb-2022. Given there was no additional clinical benefit in the doublet therapy arm compared to the monotherapy arm for the primary endpoints of PFS and ORR, the Sponsor, in consultation with

the DMC, has decided to unblind the trial, and no additional OS formal analyses will be performed. Any further efficacy analyses, if conducted, will be descriptive.

10.1 Sample Size Determination

The sample size of the study accounts for the three primary efficacy endpoints: ORR, PFS and OS. The overall alpha for this study is 0.05, which is split with 0.001 to evaluate ORR, 0.03 to evaluate PFS and 0.019 to evaluate OS. All alphas are two-sided. ORR will be analyzed when the first 480 randomized participants have a minimum follow-up of 6 months. PFS will be evaluated for treatment effect at an alpha of 0.03 with at least 90% power; no interim analysis of PFS is planned. OS will be evaluated for treatment effect at an alpha level of 0.019.

A fallback approach will be used to test ORR, PFS, and OS. If ORR is significant, the alpha of 0.001 allocated to ORR will be passed to OS. If PFS is significant, the alpha of 0.03 allocated to PFS will pass to OS. That is,

- If both ORR and PFS are significant, then OS will be tested at 0.05 level
- If PFS is significant but ORR is not, then OS will be tested at 0.049 level
- If ORR is significant but PFS is not, then OS will be tested at 0.02 level
- If neither ORR nor PFS is significant, then OS will remain to be tested at 0.019 level

It is estimated that approximately 764 previously untreated metastatic melanoma subjects will be randomized into two arms in a 1:1 ratio. Table 10.1-1 summarizes sample size design parameters and schedule of primary endpoint analyses planned in this study.

Table 10.1-1: Summary of Sample Size Parameters and Schedule of Analyses

Endpoints	ORR	PFS	OS
Sample size	480: 240 vs 240	764: 382 vs 382	764: 382 vs 382
Power	90%	90%	90%
Alpha	0.1% (2-sided)	3% (2-sided)	1.9% (2-sided)
Alternative Hypothesis: Experimental vs Control	ORR: 66% vs 45%	PFS rates for nivolumab arm: 63% (3 months) 52% (6 months) 46% (9 months) 37% (18 months) HR=0.7	mOS: 53.7 months vs 37.6 months HR=0.7
ORR Final	~35.9 months (29.9 months of accrual + 6 months of follow-up)	--	--
PFS Final Analysis/OS Interim #1	--	~39.8 months 375 PFS events Critical HR: 0.799	~39.8 months Critical HR corresponds to two-sided alpha = 0.0001,

Table 10.1-1: Summary of Sample Size Parameters and Schedule of Analyses

Endpoints	ORR	PFS	OS
			and depends on the number of OS events observed
OS Interim #2	--	--	~47.9 months 230 OS events (55% of OS Information) Critical HR: 0.646
OS Interim #3	--	--	~59 months 314 OS events (75% of OS Information) Critical HR: 0.729
OS Final Analysis	--	--	~76.3 months 419 OS events Critical HR: 0.792

Note: Analysis time projections are updated based on updated enrollment projection in February, 2021. If final ORR and final PFS analyses occur close enough, they may be combined into one analysis conducted at the final PFS analysis time. In this case, the ORR formal analysis will only be conducted for the ORR population.

10.1.1 Sample Size Justification for ORR Estimate

Given a two-sided alpha of 0.001, 480 subjects in nivolumab+bempegaldesleukin and nivolumab arms will provide approximately 90% power to detect 21% ORR difference between the 2 treatment arms, assuming ORRs of 66% and 45%, respectively, using a Chi-square test. If observed ORR difference is greater than 14.9%, it will result a statistically significant result.

This ORR formal comparison will occur when the first 480 randomized participants have a minimum follow-up of 6 months. In the original protocol, the ORR formal comparison was projected to occur approximately 15.6 months after the first subject's randomization date (9.6 months of accrual of 480 subjects and 6 months of ORR follow-up). That projection was based on the assumption that the accrual duration of the study was approximately 15 months.

Based on actual enrollment and updated projection in February 2021, where the accrual duration of the study is projected to be approximately 38.8 months, the ORR formal comparison is projected to occur approximately 35.9 months from the first subject's randomization date (~29.9 months of accrual of 480 subjects and 6 months of ORR follow-up). If final ORR and final PFS analyses occur close enough, they may be combined into one analysis conducted at the final PFS analysis time. In this case, the ORR formal analysis will only be conducted for the ORR population.

10.1.2 Sample Size Justification for PFS Comparison

Based on the PFS results for nivolumab from BMS Study CA209067 (ie, the CheckMate-067 Study,³⁶ a non-constant PFS hazard was observed. Thus, for the sample size calculation, a piecewise exponential distribution was assumed in each treatment arm with a constant HR of 0.7. Specifically, in the nivolumab arm we assume PFS rates of 63%, 52%, 46%, and 37% at 3, 6, 9,

and 18 months, respectively. Under the assumptions of piecewise exponential distribution for each arm and a constant HR of 0.7, the calculated median progression-free survival (mPFS) are 6.96 months and 17.8 months for the nivolumab and nivolumab+bempegaldesleukin arms, respectively. At a two-sided alpha level of 0.03, a total of 375 PFS events are needed to detect a PFS hazard ratio (HR) of 0.7 with 90% power. In the original protocol, under the assumption of 15 months of enrollment period, 7-months of minimum follow-up, and a 10% annual drop-out rate, a total sample size of 764 subjects is required to observe the needed 375 PFS events at 22 months. Under updated projection in February 2021, with 764 subjects and 10% annual drop-out rate, the PFS analysis time, ie, to observe approximately 375 PFS events, is projected to occur at approximately 39.8 months from the first subject's randomization date. It is projected that an observed HR of 0.799 or less would result in a statistically significant improvement in the final analysis of PFS.

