Pregnancy Test	X			X		X	Serum or urine pregnancy test (minimum sensitivity equivalent units 25 IU/L or equivalent units of HCG) is required within 24 hours prior to treatment in women of childbearing potential (WOCBP).
Clinical Laboratory Testing	X			X		X	Refer to Section 9.4.5 Clinical Safety Laboratory Assessments for list of laboratory tests See Table 9.4.5-1 . Hematology and chemistry assessments scheduled for the day of study drug(s) dosing must be available and assessed before dosing. Hematology and chemistry assessments can be drawn within 72 hours prior to dosing, though renal function (ie, serum creatinine) must be assessed within 24 hours prior to dosing with bempegaldesleukin or as soon as locally feasible. For the first dose visit, labs need not be repeated if they were performed within 72 hours and the results are available and have been reviewed for eligibility.

Table 2-2: On-Study Activities (CA045001)

*Per Protocol Amendment 03, the text below related to bempegaldesleukin is not applicable.

Procedure	Cycle 1 Only ^a			Cycle 2 Only ^a		Cycle 3 and Beyond ^a	Notes
	Day 1	Day 3-5	Day 8 (± 1 day)	Day 1 (± 3 days)	Day 3-5	Day 1 (± 3 days)	
Efficacy Assessments							
Body Imaging	
Prior to Protocol Amendment 03, contrast-enhanced CT of the chest, CT or MRI of the abdomen, pelvis, and all known and suspected sites of disease should be performed every 9 weeks (± 7 days) from randomization up to Week 54 and then every 12 weeks (± 7 days). Per Protocol Amendment 03, tumor assessments will continue per schedule of local standard of care (SOC).
 
Tumor assessment for progression will not be based on imaging performed for biopsy in Cycle 2.
 
Tumor assessment schedule should be maintained regardless of dose delays.
 
Use same imaging method as was used at Screening.
					
Per Protocol Amendment 03, any participant remaining on treatment will continue imaging per Section 9.1.1. Imaging will be performed per SOC and images will no longer be submitted (BICR).
 
All study treatment decisions will be based on the Investigator’s assessment of tumor images.
 
See Section 9.1.1 for additional details.
	

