10.1.3 Sample Size Justification for OS Comparison

For OS, at a two-sided alpha level of 0.019, a total of 419 events are needed to detect a HR of 0.70 with 90% power. Assuming a median OS time for the nivolumab arm (Arm B) of 37.6 months, with a total sample size of 764, in the original protocol it is projected the total study duration is 59 months (15 months for accrual and 44 months for follow up), with a critical boundary hazard ratio of 0.792. With updated enrollment projection in February 2021, it is projected the total study duration (corresponding to the final OS analysis time) is approximately 76.3 months from the first subject's randomization date. All projected OS interim analysis times are updated accordingly. However, all PFS and OS analysis times are driven by the required number of events. The actual analysis times depend on actual enrollment speed and events accrual, thus may be different from projections.

Three formal interim analyses of OS are planned for this study. The first OS interim analysis is planned at the time point of the final PFS analysis, where OS will be tested at 0.0001 level, regardless of the outcome of the final PFS analysis. For instance, if 150 OS events are observed at the time point of the final PFS analysis, then the critical boundary on hazard ratio for the first OS interim is 0.53.

All other formal OS analyses will be conducted when planned number of OS events specified below are observed.

The second OS interim analysis is planned when 230 OS events are observed (55% of the targeted OS events for final analysis, projected to happen 47.9 months from FPFV), and the third OS interim analysis is planned after observing 314 OS events (75% of targeted OS events needed for final analysis, projected to happen 59 months from FPFV). Accounting for the $\alpha = 0.0001$ spent at the first OS interim, the remaining alpha level will be the overall OS alpha level (as described below) minus 0.0001 depending on the ORR and PFS results. If neither ORR nor PFS is significant, the remaining alpha level of 0.0189 ($\alpha=0.019-0.0001$) will be spent on the rest of the OS interim analyses and the final OS analysis. The stopping boundaries for the second OS interim, the third OS interim, and the final OS analyses will be derived based on the actual number of deaths using the O'Brien and Fleming alpha-spending function in software EAST 6.4.1. If the

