	
be estimated. In addition, to account for potential non-proportional hazard for PFS, sensitivity analyses will be conducted to compare PFS per BICR between treatment groups using weighted log-rank test. Technical details will be given in the SAP.
 
Participants who do not progress or die will be censored on the date of their last evaluable tumor assessment. Participants who do not have any on-study tumor assessments and do not die will be censored on their date of randomization. Participants who started a new anticancer treatment regimen prior to disease progression will be censored on the date of their last evaluable tumor assessment prior to receiving the new antineoplastic regimen. Participants who are lost to follow up will be censored on the date of their last evaluable tumor assessment.

Primary Overall Survival
	
Overall survival (OS) is defined as the time between the date of randomization and the date of death due to any cause. Participants who do not have a date of death will be censored on the last date for which a participant was known to be alive. OS will be analyzed using the stratified log rank test, Cox proportional hazards model, and Kaplan Meier method, similar to PFS. The OS rates at 12 and 24 months will also be estimated. In addition, similar sensitivity analyses to account for potential non-proportional hazard for OS will also be conducted.

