10.3.4 Interim Analyses

Several interim analyses are planned for this study. Table 10.3.4-1 gives an overview of their purposes and timing. The final ORR and PFS analyses, and the first OS interim analysis (combined with the second OS interim analysis) have been completed using the locked database with a database lock date of 01-Feb-2022. Given there was no additional clinical benefit in the doublet therapy arm compared to the monotherapy arm for the primary endpoints of PFS and ORR, the Sponsor, in consultation with the DMC, has decided to unblind the trial. No additional OS formal analyses will be performed. Any further efficacy analyses, if conducted, will be descriptive.

Table 10.3.4-1: Interim Analyses Schedule

Analysis	Purpose	Analysis Trigger
Final ORR Analysis	Demonstrate significant improvement in ORR	Approximately the first 480 randomized participants have a minimum of 6-month of follow-up
Final PFS Analysis, Interim OS Analysis #1	Demonstrate significant improvement in PFS and OS	~375 PFS events
Interim OS Analysis #2		~230 OS events
Interim OS Analysis #3	Demonstrate significant improvement in OS	~314 OS events
^a Final OS Analysis		~419 OS events

^a If the 419th OS event has not occurred 60 months after randomization of the last participant, then the final OS analysis will take place at that time. In such case, the final analysis boundary will be re-calculated based on the observed final number of events using all remaining alpha for OS.

The Statistical Analysis Plan will further describe the planned interim analyses.

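### Should the final PFS analysis, triggered by about 375 events alone, also have required a minimum follow-up?

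*Combined protocol and SAP*

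**What the plan says.** Section 10.1.2 describes the design model: "a piecewise exponential distribution was assumed in each treatment arm with a constant HR of 0.7". From it come 375 events, 90% power at two-sided alpha 0.03, and a critical HR of 0.799. The original projection used 15 months of enrollment and "7-months of minimum follow-up", giving 22 months in total. Section 10.1.1 updates this: "the accrual duration of the study is projected to be approximately 38.8 months", with 480 participants randomized by about 29.9 months. Section 10.1.2 then gives the updated PFS analysis time as the time "to observe approximately 375 PFS events, is projected to occur at approximately 39.8 months" after the first randomization.

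The trigger is a count. Table 10.3.4-1 gives approximately "375 PFS events" with no second condition, and Section 10.1.3 says that "all PFS and OS analysis times are driven by the required number of events".

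In Section 10.3.1 the primary PFS test is an unweighted stratified log-rank test. A weighted version is added as a sensitivity analysis: "to account for potential non-proportional hazard for PFS, sensitivity analyses will be conducted". No power is given for that situation. Table 2-2 schedules body imaging (before Amendment 03) "every 9 weeks (± 7 days) from randomization up to Week 54".

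**The concern.** The trigger stayed at 375 events while accrual stretched from 15 to 38.8 months, so the projected minimum follow-up fell from 7 months to about 1 month. The last participants would not yet have reached their first scan. If the experimental arm does no better than control, events come faster and the count can be reached before accrual ends.

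Under proportional hazards this does not matter, because the power of the log-rank test depends on the number of events. Under non-proportional hazards it also depends on when they occur. On the plan's PFS rates, 62-64% of the 375 events at HR 0.7 fall within 3 months of randomization. If the curves separated only at the first scan or later, many events would carry no treatment difference. A real benefit could then be missed on the endpoint that holds alpha 0.03 and passes it to OS.

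**Working it through.** **1. The plan's own figures.** Inputs from Section 10.1.2: HR 0.7, two-sided alpha 0.03 (z = 2.170), power 90% (z = 1.282), 1:1 allocation.

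- Events = 4(2.170 + 1.282)² / (ln 0.7)² = 4 × 11.914 / 0.12721 = 374.6, rounded up to 375.
- Critical HR = exp(−2 × 2.170 / √375) = 0.799.
- Piecewise-exponential medians from 63/52/46/37% at 3/6/9/18 months: 6.96 and 17.83 months (stated 6.96 and 17.8).

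All agree.

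**2. Follow-up left.** 39.8 − 38.8 = 1.0 month. The first scan, at 9 weeks, is about 2.1 months after randomization.

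**3. When the 375th event falls.** Inputs: 764 participants, 10% annual drop-out, 480 randomized by 29.9 months and 764 by 38.8. The accrual curve and the hazard after month 18 are not given, so ranges span plausible shapes.

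- HR 0.7: 39.1-40.7 months; before accrual ends in roughly 2-39% of simulated trials.
- HR 0.85: 37.9-39.1 months.
- HR 1.0: 36.9-38.1 months, with 703-739 of 764 randomized; before accrual ends in 87-100%.

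**4. Does slower accrual reduce power?** Both schedules must be cut at the same count. The delayed patterns are assumptions, scaled to keep the planned 18-month PFS: 0.37^0.7 = 0.499 against 0.37. With no difference before 3 months, 0.63 × (0.37/0.63)^h = 0.499 gives h = 0.44. With no difference before 9 weeks, h = 0.56. Power is from simulation of an unstratified log-rank test with 2,000-4,000 trials per cell (standard error at most √(0.25/2000) = 1.1 points).

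| At the 375th event | Original 15-month accrual | Updated 38.8-month accrual |
|---|---|---|
| Constant HR 0.7 | 91% | 88-90% |
| No difference to 9 weeks, then HR 0.56 | 63-66% | 62-69% |
| No difference to 3 months, then HR 0.44 | 43% | 49-57% |
| HR 0.7 to month 6, then 1.0 | 75% | 66% |
| Median follow-up at HR 0.7 (months) | about 12 | 13.5-15.5 |
| Events within 3 months at HR 0.7 | 65% | 62-64% |

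Slower accrual moves events later in patient time, not earlier. It helps or leaves unchanged the delayed cases, and it costs power when an effect wanes.

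**5. What a floor would buy.** Floors run from the last randomization: 38.8 + 2.1 = 40.9 months, 38.8 + 4.1 = 42.9, and 38.8 + 7 = 45.8.

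| Cut | 9-week delay | 3-month delay | Null readout later by |
|---|---|---|---|
| 375 events only | 62-69% | 49-57% | – |
| and 9 weeks | 65-74% | 52-64% | 2.8-4.0 months |
| and 18 weeks | 71-80% | 59-73% | 4.9-6.0 months |
| and 7 months | 75-84% | 66-78% | 7.7-8.9 months |

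Under constant HR 0.7 the 9-week floor adds about 1-2 points. For early effects even 7 months does little: HR 0.6 to month 6 then 0.9 stays at 96-97%; HR 0.6 then 1.0 goes from 93-94% to 93%; HR 0.7 then 1.0 goes from 65.9% to 67.5%.

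**6. Type I error.** With the cut at the 375th event, simulated one-sided rejection under HR 1.0 was 1.2-1.7%, against a nominal 1.5%.

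**7. The executed analysis.** The reported 97% CI of 0.88-1.35 gives SE = ln(1.35/0.88) / (2 × 2.170) = 0.0986, hence 4 / 0.0986² ≈ 411 events (394-430 allowing for rounding). The first two OS interims were combined, which Section 10.1.3 provides for only with at least 230 deaths at the final PFS analysis, a count projected for 47.9 months. Both suggest a cut later than a bare 375 events at 39.8 months.

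**The case for a change.** The best case for a floor is that the plan attaches time conditions elsewhere (6 months of follow-up for ORR, a 60-month limit for final OS) but none to PFS, which holds most of the alpha. It anticipates non-proportional hazards yet gives no power for them. The original 22-month cut, simulated as a fixed date, gives 91%, 73% and 59% in the constant, 9-week and 3-month cases, and a 9-week floor moves the stated cut by only 40.9 − 39.8 = 1.1 months.

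The facts stand, but the inference is weaker. ORR is not event-driven and needs a follow-up rule to be defined; the OS limit is a ceiling, not a floor. The 22-month figures rest on 393-399 events, and Section 10.1.2 offers 22 months as the time when 375 events would be seen, not as a fixed date. Cut at 375, that schedule does no better than the updated one. The sensitivity to a constant HR comes from the design model and the unweighted test, and no floor examined restores 90% in the delayed cases.

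Two points survive. A power figure under one delayed pattern would have been informative, and a report should give PFS events, participants randomized and minimum follow-up at the actual cut. Both add detail without altering the plan.

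**Conclusion.** No change is called for. An event-count trigger with power stated under the assumed alternative is ordinary practice, and every stated figure is correct on its own terms. A floor is a choice the sponsor could reasonably decline: about 2 to 8 points of power at 9 weeks if the effect is delayed, little or nothing if it is early, and a null readout 2.8 to 4.0 months later. New trigger wording could not affect the result, because the final PFS analysis was completed on the database locked on 01-Feb-2022 (HR 1.09).

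This rests on assumed delay patterns, assumed accrual shapes consistent with the two stated accrual points, and an assumed hazard after month 18. The file reviewed holds the protocol text; Section 10 defers detail to separate SAP text that is not in it, so a data-cut rule there cannot be excluded. Such a rule would only weaken the concern further.
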